6.10.1 Intra-Patient Escalation

A recent FDA review concluded that incorporation of a step dose / IPE can result in better patient tolerance of higher doses of CD3 bispecific molecules ([Saber, 2017](#)) due to a phenomenon of induced tolerance or tachyphylaxis. IPE regimens are used for the related ImmTAC molecule tebentafusp as well as the approved CD3 bispecific blinatumomab.

If the severity of cytokine-mediated AEs tend to become less severe following the initial doses of study drug using a fixed-dose regimen, the SST may initiate a 1-step IPE regimen, in which a lower dose is given on Cycle 1 Day 1 and a higher (target) dose is given on Cycle 1 Day 8 and beyond, as shown in [Figure 6-1](#).

[figure not shown]

Figure 6-1: Schematic Illustration of a 1-Step IPE Regimen

Rules for the 1-step IPE regimen are as follows:

- The initial target dose level must be a permitted escalation step based on BLRM output and the consensus of the SST
- The initial target dose level must not exceed the fixed-dose MTD (if established)
- The C1D1 dose level must be at least one dose level below the initial target dose, and must be a dose level that has been evaluated in ≥ 3 patients using a fixed-dose regimen, with a decision to escalate based on the BLRM output and SST review of all available relevant data.
- Escalation of the target dose in subsequent cohorts may proceed as in the main dose escalation:
 - Separate MTD/RP2D may be identified using fixed-dose and 1-step IPE regimens
 - DLT will be attributed to the dose level of the most recently administered dose prior to onset of the DLT (eg, a DLT with onset on C1D4 would be attributed to the C1D1 dose level, while a DLT with onset on C1D10 would be associated to the C1D8 dose level)
- The dose level for C1D1 remains fixed for all subsequent cohorts
- Patients receiving IPE must receive the C1D1 dose prior to receiving the target dose
- If a 1-step IPE regimen is evaluated in Phase I, it may be selected for further evaluation in Phase II

Experience with other CD3 bispecific molecules (including tebentafusp and blinatumomab) indicates that multi-step IPE may mitigate the risk of a cytokine-mediated AE more effectively than a 1-step IPE or fixed-dose regimen. If further mitigation of cytokine-mediated events is desired, the SST may decide to evaluate a two-step IPE regimen, in which an intermediate dose is given on Cycle 1 Day 8, as shown in [Figure 6-2](#).

[figure not shown]

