7.2 Treatment Period Schedule

The treatment period starts with Day 1 of Cycle 1 (C1D1). A treatment cycle is defined as 28 days for the purposes of scheduling procedures and evaluations.

Any assessments required on C1D1 that are also performed as part of Screening do not need to be repeated on C1D1 if the data were obtained 72 hours prior to the first dose of study treatment. For subsequent visits, pregnancy testing may be performed up to 72 hours prior to dosing and other safety assessments may be performed up to 24 hours prior to dosing.

During the study visits, all tests and/or procedures should occur on schedule whenever possible. A visit window of ± 7 days (with a minimum of 7 days between doses of IMCnyeso) is allowed unless otherwise indicated in the protocol. If study drug infusions are delayed, the assessments associated with those infusions should be rescheduled accordingly. However, the timing of protocol-specified radiological assessments should be calculated in weeks using C1D1 as reference and should not be adjusted because of delays in treatment.

Assessments required during the treatment period are presented by visit in [Table 7-2](#). For patients receiving IPE, follow the alternate Cycle 1 schedule provided in [Section 13.4](#). Assessments marked “X” should be performed prior to dosing. Assessments that are to be performed at multiple timepoints are marked with the number of timepoints (including optional timepoints, if applicable) for the visit (eg, 2 \times is twice) and details of the timepoints are provided in the footnote. Additional details regarding the assessments are provided in [Section 7.4](#). Please refer to [Section 6](#) for dosing details. Patients will continue treatment until they meet criteria for discontinuation, as described in [Section 6.16](#).

Table 7-2: Schedule of Treatment Period Assessments

Procedure	Cycle 1						Cycle 2				Cycle 3				Later Cycles			
Day of Cycle	1	2	8	9	15	22	1	8	15	22	1	8	15	22	Visits on Days 1, 8, 15, and 22			
Adverse events	X	X	X	X	X	X	X	X	X	X	X	X	X	X		X		
Concomitant medications	X	X	X	X	X	X	X	X	X	X	X	X	X	X		X		
Safety Assessments																		
Complete physical examination	X																	
Abbreviated physical examination			X		X	X	X	X	X	X	X	X	X	X		D1 of each cycle		
Weight	X						X				X						D1 of each cycle	
Vital signs	~14x	~14x		3x	3x	3x	3x	3x	3x	3x	3x	3x	3x	3x		3x each dosing day		
12-lead ECG (single)	2x						2x				2x					2x on C4D1, C5D1, and C6D1		

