ECOG performance status	X											X					D1 of each cycle	
Hematology panel	X	X	X	X	X	X	X	X	X	X	X		X				D1 of each cycle	
Chemistry panel	X		X		X	X	X	X	X	X	X		X				D1 of each cycle	
Thyroid function	X						X				X							
Urine pregnancy test (women of childbearing potential)	X						X				X						D1 of each cycle	
PK and Immunogenicity																		
Pharmacokinetic sampling	8x	3x	8x	X	4x	4x	2x		2x		2x		2x			2x on D1 of odd-numbered cycles		
Immunogenicity sampling	X		X		X		X				X						D1 of odd-numbered cycles	
Disease Assessment																		
CT/MRI scans and disease assessment												X				Q8W to W40 (C3, C5, C7, C9, C11), then Q12W (C14, C17, etc)		
Tumor biopsy	Between C1D9 and C1D16 (required for ≥ 10 patients in Phase II, optional for all other patients) Optional for all patients at time of progression																	

IMCnyeso administration	X		X		X	X	X	X	X	X	X	X	X	X	D1, D8, D15, and D22 of each cycle
-------------------------	---	--	---	--	---	---	---	---	---	---	---	---	---	---	------------------------------------

AE = adverse event; C#D# = Cycle # Day #; [REDACTED]; CT = computerized tomography; ECG = electrocardiogram; ECOG = Eastern Cooperative Oncology Group; EOI = end of infusion; hr = hour(s); min = minutes; MRI = magnetic resonance imaging; [REDACTED]; PK = pharmacokinetics; Q#W = every # weeks; [REDACTED]; W = week.

ECG assessments are to be done pre-dose and within 1 hour of EOI on indicated days.

Vital signs (body temperature, pulse, respiratory rate, and blood pressure; in addition, oxygen saturation should be collected for \geq first 3 cycles of treatment) are to be assessed at the following timepoints:

- C1D1/C1D2 and C1D8/C1D9: pre-dose (within 2 hours), EOI (within 15 min), every 2 hours (\pm 15 min) through 12-hour post-EOI, every 4 hours (\pm 30 min) until discharge
- All other doses: pre-dose (within 2 hours), EOI (within 15 min), and 1-hour post-EOI (\pm 15 min)

Pharmacokinetics samples are to be collected at the following timepoints:

- C1D1 and C1D8: pre-dose (within 2 hours), EOI (within 15 min), 1-hour post-EOI (\pm 15 min), 2-hour post-EOI (\pm 15 min), 4-hour post-EOI (\pm 15 min), 6-hour post-EOI (\pm 30 min), 8-hour post-EOI (\pm 1 hr), and 12-hour post-EOI (\pm 3 hr)
- C1D2: 24-hour post-EOI (\pm 4 hr), 36-hour post-EOI (optional, \pm 4 hr), and 48-hour post-EOI (optional, \pm 4 hr)
- C1D9: 24-hour post-EOI (\pm 4 hr)

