13.4 Schedule of Cycle 1 Assessments, Intra-Patient Escalation Regimen

Patients who receive IPE should follow the schedule below during Cycle 1, and the main schedule at all other times, including Pre-Screening, Screening, Cycle 2 and subsequent treatment cycles, and Follow-up.

The Cycle 1 schedule is provided in [Table 13-13](#). Assessments marked “X” should be performed prior to dosing. Assessments that are to be performed at multiple timepoints are marked with the number of timepoints (including optional timepoints, if applicable) for the visit (eg, 2× is twice) and details of the timepoints are provided in the footnote. Additional details regarding the assessments are provided in [Section 7.4](#).

Table 13-13: Schedule of Cycle 1 Assessments, IPE Regimen

Procedure	Cycle 1						
Day of Cycle	1	2	8	9	15	16	22
Adverse events	X	X	X	X	X	X	X
Concomitant medications	X	X	X	X	X	X	X
Safety Assessments							
Complete physical examination	X						
Abbreviated physical examination			X		X		X
Weight	X						
Vital signs		~14×		~14×		~14×	3×
12-lead ECG (single)	2×						
ECOG performance status	X						
Hematology panel	X	X	X	X	X		X
Chemistry panel	X		X		X		X
Thyroid function	X						
Urine pregnancy test (women of childbearing potential)	X						
PK and Immunogenicity Assessments							
Pharmacokinetic sampling	3×	X	8×	X	8×	X	3×
Immunogenicity sampling	X		X		X		
[REDACTED]		Between C1D9 and C1D16 (required for ≥ 10 patients in Phase II, optional for all other patients)					
[REDACTED]							

Procedure	Cycle 1					
IMCnyeso Administration						
One-step IPE	C1D1 dose level		Target dose level		Target dose level	Target dose level
Two-step IPE	C1D1 dose level		C1D8 level		Target dose level	Target dose level

AE = adverse event; C#D# = Cycle # Day #; CRS = cytokine release syndrome; [REDACTED]; ECG = electrocardiogram; ECOG = Eastern Cooperative Oncology Group; EOI = end of infusion; hr = hour(s); min = minutes; [REDACTED] PK = pharmacokinetics; [REDACTED]

ECG assessments are to be done pre-dose and within 1 hour of EOI on indicated days.

Vitals (body temperature, pulse, respiratory rate, blood pressure; oxygen saturation should also be assessed for \geq first 3 cycles of treatment), are to be assessed at the following timepoints:

- C1D1/C1D2, C1D8/C1D9, and C1D15/C1D16: pre-dose (within 2 hours), EOI (within 15 min), every 2 hours (\pm 15 min) through 8-hour post-EOI, then every 4 hours (\pm 30 min) until discharge

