- C1D22: pre-dose (within 2 hours), EOI (within 15 min), and 1-hour post-EOI (\pm 15 min)

Pharmacokinetics samples are to be collected at the following timepoints:

- C1D1: pre-dose (within 2 hours), EOI (within 15 min), 8-hour post-EOI (\pm 1 hr)
- C1D8 and C1D15: pre-dose (within 2 hours), EOI (within 15 min), 1-hour post-EOI (\pm 15 min), 2-hour post-EOI (\pm 15 min), 4-hour post-EOI (\pm 15 min), 6-hour post-EOI (\pm 30 min), 8-hour post-EOI (\pm 1 hr), and 12-hour post-EOI (optional, \pm 3 hr)
- C1D2, C1D9, and C1D16: 24-hour post-EOI (\pm 4 hr)
- C1D22: pre-dose (within 2 hours), EOI (within 15 min), 8-hour post dose (\pm 1 hr)

Central lab cytokine testing samples are to be collected at the following timepoints:

- C1D1: pre-dose (within 2 hours) and 4-hour post-EOI (\pm 15 min)
- C1D8 and C1D15: pre-dose (within 2 hours), 4-hour post-EOI (\pm 15 min), 8-hour post-EOI (\pm 1 hr), and 12-hour post-EOI (optional, \pm 3 hr)
- C1D2, C1D9, and C1D16: 24-hour post-EOI (\pm 4 hr)
- C1D22: pre-dose (within 2 hours) and 4-hour post-EOI (\pm 15 min)
- Additional samples may be collected if a patient has suspected CRS. Recommended timepoints are within 5 hours and 1 week after onset of CRS.

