8.4 Vital Signs

Vital signs (body temperature, pulse, respiratory rate, and blood pressure) will be performed as scheduled (details see Table 7-2 of the protocol V4.0).

Vital signs pre-dose values and worst absolute values and changes from pre-dose as well as time from start of infusion to worst will be summarized for each dose. See Section 9 of the protocol V4.0 for definition of observation periods.

The relevant vital sign values at each visit will be classified into the categories of low, normal, and high based on the following reference ranges.

- Systolic blood pressure, low is <75 mm Hg or decrease of ≥ 30 mm Hg that results in ≤ 90 mm Hg. High is ≥ 160 mm Hg. (CTCAE V4.03, Grade 1: Prehypertension (systolic BP 120 - 139 mm Hg), Grade 2: Stage 1 hypertension (systolic BP 140 - 159 mm Hg), Grade 3: Stage 2 hypertension (systolic BP ≥ 160 mm Hg))
- Diastolic blood pressure, low is <40 mm Hg or decrease of ≥ 20 mm Hg that results in ≤ 50 mm Hg. High is ≥ 100 mm Hg. (CTCAE V4.03, Grade 1: Prehypertension (diastolic BP 80 - 89 mm Hg), Grade 2: Stage 1 hypertension (diastolic BP 90 - 99 mm Hg), Grade 3: Stage 2 hypertension (diastolic BP ≥ 100 mm Hg))
- Pulse, low is <60 bpm. High is >100 bpm.
- Temperature, low is ≤ 32 °C. High is ≥ 38 °C for any fever and >40 °C for CTCAE grade 3 fever. (CTCAE V4.03, 1. Fever- Grade 1: 38.0 - 39.0 degrees C, Grade 2: >39.0 - 40.0 degrees C, Grade 3: >40.0 degrees C for ≤ 24 hours, Grade 4: >40.0 degrees C for > 24 hours; 2. Hypothermia- Grade 2: 35 - >32 degrees C; Grade 3: 32 - >28 degrees C; Grade 4: ≤ 28 degrees C)
- Weight gain: grade 1 = 5 - <10% from baseline, grade 2 = 10 - <20% from baseline, grade 3 = $\geq 20\%$ from baseline.
- Weight loss: grade 1 = 5 - <10% from baseline, grade 2 = 10 - <20% from baseline, grade 3 = $\geq 20\%$ from baseline.
- Oxygen saturation, low is < 94% and <88% is Grade 3.

For those parameters where the values might go in multiple directions (low/high), the results will be presented for worst low post-baseline and worst high post-baseline results separately. Figures for vitals during cycle 1, with all timepoints from pre-dose through ~24 hours post-dose will be plotted.

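### SAP 8.4 takes the worst vital sign per dose over unequal numbers of readings, so later fixed doses look milder even when nothing has changed

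*SAP*

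**What the plan says.** SAP 8.4 states that "worst absolute values and changes from pre-dose as well as time from start of infusion to worst will be summarized for each dose". For the schedule it says that vital signs "will be performed as scheduled (details see Table 7-2 of the protocol V4.0"). It refers to protocol Section 9 for observation periods, but that section sets no per-dose window for vital signs.

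Protocol Table 7-2 gives about 14 sets of readings around each of the first two fixed doses: "C1D1/C1D2 and C1D8/C1D9: pre-dose (within 2 hours), EOI (within 15 min), every 2 hours" to 12 hours after end of infusion (EOI), then every 4 hours until discharge. From the third dose the footnote reads "All other doses: pre-dose (within 2 hours), EOI (within 15 min), and 1-hour post-EOI", and the later-cycle entry is "3x each dosing day".

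IPE patients follow Table 13-13 in Cycle 1, which SAP 8.4 does not cite. It has "C1D1/C1D2, C1D8/C1D9, and C1D15/C1D16: pre-dose (within 2 hours), EOI (within 15 min), every 2 hours" to 8 hours, then every 4 hours until discharge. Only the fourth dose is sparse: "C1D22: pre-dose (within 2 hours), EOI (within 15 min), and 1-hour post-EOI".

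SAP 8.4 also plans Cycle 1 figures by timepoint to about 24 hours. The one vital-signs table listed in SAP 14.2 is of observed values and change from baseline; no worst-per-dose table is listed.

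**The concern.** The minimum of many readings is lower on average than the minimum of two from the same distribution, and the maximum is higher. A per-dose table of worst values therefore mixes any drug effect with the number of times the patient was measured. In fixed-dose patients the count falls sharply between dose 2 and dose 3. At C1D15 it is low for fixed-dose patients and still high for IPE patients.

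Time to worst has the same defect. On scheduled readings at a later dose it cannot exceed the infusion time plus about 1 hour.

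Changes in vital signs are among the listed Phase I primary endpoints and Phase II secondary endpoints. A reader of the study report could take the per-dose summary as evidence that tolerance develops with repeat dosing, or that one regimen is harder on blood pressure than the other.

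**Working it through.** **Step 1: reproduce the schedule's count.** On the fixed regimen with discharge 36 h after EOI: 1 pre-dose + 1 EOI + 6 (2-hourly to 12 h) + 6 (4-hourly, 16 to 36 h) = 14, the Table 7-2 entry. Later doses: 1 + 1 + 1 = 3. After the pre-dose reading this is 13 against 2.

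**Step 2: post-dose counts by discharge time.**

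| Discharge after EOI | Fixed, dense day | IPE, dense day |
|---|---|---|
| 8 h (Phase II option) | 5 | 5 |
| 24 h | 10 | 9 |
| 36 h | 13 | 12 |
| 48 h | 16 | 15 |

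Protocol 6.2 gives two nights after C1D1 and one after C1D8, so about 13 fits dose 1 and about 10 fits dose 2.

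**Step 3: expected worst low reading with no true change.** For n independent normal readings, in within-patient SD units:

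E[min] = −∫ x · n · φ(x) · Φ(x)^(n−1) dx

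| n | E[min] | Gap against n = 2 |
|---|---|---|
| 2 | −0.564 | 0 |
| 5 | −1.163 | 0.60 |
| 9 | −1.485 | 0.92 |
| 10 | −1.539 | 0.98 |
| 13 | −1.668 | 1.10 |

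Worst high readings shift by the same amounts upward. The expected pre-dose value is the same at every dose, so the worst change from pre-dose shifts equally.

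**Step 4: convert to mmHg.** The SD is assumed at 8 to 12 mmHg.
- Lower end, 10 readings: 0.975 × 8 = 7.8.
- Upper end, 13 readings: 1.104 × 12 = 13.2.
- Eight-hour monitoring, 5 readings: 0.599 × 8 = 4.8 to 0.599 × 12 = 7.2.
- C1D15, IPE with 9 readings against fixed with 2: 0.921 × 8 = 7.4 to 0.921 × 12 = 11.1.
- C1D1 against C1D8 in fixed-dose patients (13 against 10): 1.668 − 1.539 = 0.13 SD, so even these two doses are not exactly alike.

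**Step 5: serial correlation.** In simulation of 13 against 2 readings at SD 10, the gap in mean worst change is 11.0 to 12.4 mmHg for hourly correlation from 0 to 0.9. Correlation does not remove it.

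**Step 6: what a reader would see.** Assume mean systolic 125, between-patient SD 12, within-patient SD 10, independent readings, 13 against 2.
- A fall of 20 mmHg or more occurs on 38% against 13% of doses. In the 15 fixed-dose patients of SAP Table 1 (4 + 3 + 5 + 3) that is 15 × 0.38 = 5.7 against 15 × 0.13 = 2.0 patients.
- The SAP low-systolic flag occurs on 2.4% against 0.4%, or 0.36 against 0.06 patients. Flag counts would barely move.

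**Step 7: does matching remove it?** Taking the worst over EOI and the first later reading at each dose, with independent readings, gives mean worst change −5.7 against −5.6 mmHg at SD 10 (differences of 0.02 at SD 8 and 0.17 at SD 15, within simulation error). The first later reading is at 2 h on dense days and 1 h on later doses, so correlation leaves a small residue. For two readings with correlation r, E[min] = −√((1 − r)/π). With hourly correlation ρ the residue is √((1 − ρ²)/π) − √((1 − ρ)/π):
- ρ = 0.5: 0.489 − 0.399 = 0.09 SD
- ρ = 0.8: 0.339 − 0.252 = 0.09 SD
- ρ = 0.9: 0.246 − 0.178 = 0.07 SD

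Each is under 1 mmHg at SD 10.

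**The case against.** **No comparison is planned.** SAP 4 says that no formal hypotheses will be tested, and 8.4 summarises each dose without defining a contrast. This stands: the issue is a side-by-side descriptive reading. A per-dose layout invites that reading, and pooling Phase I groups around the RP2D (SAP 4.2.1) does not prevent it.

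**IPE against fixed at C1D15 is confounded anyway.** The doses mostly differ: 100, 180 or 300 mcg under IPE, 3 to 100 mcg fixed. This is true, and unequal reading counts add a second distortion.

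**Unscheduled readings.** Protocol 7.4.4 allows extra readings if medically indicated, Grade 1 CRS leads to close observation, and Grade 2 CRS requires an overnight stay for the next dose. So the limit on time to worst applies to scheduled readings only. Extra readings depend on clinical events, so they do not equalise the schedules.

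**Timing of reactions.** The 4 to 24 hour range in protocol 1.4 is for tebentafusp. The Amendment 3 rationale says that CRS signs with IMCnyeso arose within a few hours. The range should not be used to claim that late falls at later doses are being missed; the point does not need it.

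**Existing displays.** The Cycle 1 figures by timepoint help, but they correct neither the worst-value nor the time-to-worst summary and do not extend beyond Cycle 1.

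**A stronger inference.** A reader might conclude that the artefact feeds the IPE decision, since protocol 6.10.1 opens with "If the severity of cytokine-mediated AEs tend to become less severe following the initial doses of study drug". The documents do not support this. The trigger is adverse-event severity as judged by the safety team, CRS grade depends on fever and treatment given, and SAP Table 1 shows 5 and 4 patients already enrolled in IPE cohorts 5 and 6.

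**Conclusion.** The point holds for the descriptive summary. With no true change, scheduled reading counts alone make the expected worst value about 1.0 to 1.1 within-patient SD more extreme on dense fixed-dose days than at later doses. The gap is 0.6 SD with eight-hour monitoring, and about 0.9 SD at C1D15 for IPE against fixed after a 24-hour stay. The direction needs only equal variability across doses; the SD multiples assume roughly normal readings. The range of 8 to 13 mmHg rests on an assumed SD of 8 to 12 mmHg.

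Mean worst change and the proportion with a moderate fall would shift visibly; counts of the SAP low flag would not. The effect is confined to interpretation of a listed endpoint in the study report. It does not reach dose escalation: the Phase I primary variable is DLT occurrence analysed by the BLRM, which this summary does not enter.

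**What to change.** In SAP 8.4:

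- Show full-window worst value, change and time to worst side by side only for doses on the same monitoring schedule and window, for example truncated at a common post-EOI time. At 8 h both dense schedules have the same five scheduled readings (EOI, 2, 4, 6 and 8 h).
- Report the number of readings behind each per-dose summary.
- Across doses, regimens or phases, tabulate values and change from pre-dose by nominal time, or take the worst over EOI plus the first post-EOI reading, with a footnote that this is 2 h on dense days and 1 h on later doses. Only pre-dose and EOI are strictly common to all doses.
- Do not compare time to worst between different schedules.
- Cite protocol Table 13-13 alongside Table 7-2 for the IPE cohorts.

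The cost is SAP wording and one derived variable, with no new data. The downside is that the matched summary ignores later readings; these remain in the same-schedule full-window summary.

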8.5 Electrocardiogram

A standard 12-lead ECG will be performed as per the assessment schedule in Table 7-2: Schedule of Treatment Period Assessments of the protocol V4.0.

PR Interval (msec), RR Interval (msec), QRS Duration (msec), QT Interval (msec), QTcF interval (msec), QTcF derivations (formula $QTcF = QT \text{ interval} / \text{Cube Root of RR interval (seconds)}$, when required), absolute values and change from baseline will be summarized.

QTcF interval absolute values will also be tabulated by the following groups:

- ≤ 450
- $>450 - \leq 480$ msec (Grade 1)
- $>480 - \leq 500$ msec (Grade 2)
- >500 msec (Grade 3).

Change from Baseline in QTcF interval will be classified as:

- ≤ 30 msec increase from baseline
- $>30 - \leq 60$ msec increase from baseline
- >60 msec increase from baseline

A shift table of baseline QTcF to worst on-treatment results will be presented. For rating the worst on-treatment value, the following categories will be used based on the varying degrees of abnormality above, in the order of least to most severe (top to bottom):

- Missing result
- ≤ 450 msec (i.e. 'Normal')
- $>450 - \leq 480$ msec (Grade 1)
- $>480 - \leq 500$ msec (Grade 2)
- >500 msec (Grade 3)

8.6 Dose Interruptions and Reductions

The number of IMCnyeso dose interruptions, dose reductions, escalations and re-escalations will be summarized. A dose is considered interrupted when it is not administered for any reason during a visit (i.e. investigator answers the question in eCRF: "If No, reason for dose interruption"), when a visit is delayed by ≥ 7 days or omitted, or if an infusion is started and then stopped part-way through. If the dose is administered, but the investigator states it is reduced compared to last visit or if there is a reduction compared to the planned dose (for example, if a patient is assigned to 30/100/300 and receives 30 mcg on C1D8 that is a reduction from the planned dose of 100 mcg.), then the dose is considered as reduced (i.e. the investigator' answers the question in eCRF: "If Yes, reason for dose reduction").

Reasons for dose interruptions and dose reductions will be listed by patient and summarized.

9 Efficacy Analysis

Analysis of efficacy endpoints will be performed using the FAS and PPS for Phase II and only on FAS for Phase I.

No sensitivity or exploratory analysis are planned.

